3.1 Safety Analysis Sets

Safety Set

All subjects who

- have signed an informed consent form, undergone screening procedure(s) and received a subject number,
- received a study vaccination,
- provided post vaccination safety data.

Safety per protocol set

All subjects in the safety Set with the exclusions of the following cases:

- (1) Subjects administered prior to the contract date.
- (2) Subjects who didn't receive MenACWY-CRM.
- (3) Follow-up failure: The subjects whose safety information cannot be identified due to follow-up loss.
- (4) Not applicable to the indication of study drug
[Indication]
- To prevent invasive meningococcal disease caused by Neisseria meningitides serogroups A, C, Y and W-135 in persons 2 months through 55 years of age.
- (5) Subjects who violate of Protocol: Those who do not meet one item at least of the inclusion/exclusion criteria.
[Inclusion criteria]
 - 1) Male and female subjects from 2 months to 55 years of the age at the time of Visit 1 (including all 55 years old subjects, up to one day before their 56th year birthday), who are scheduled to receive vaccination with MenACWY-CRM conjugate vaccine, according to the local prescribing information and routine clinical practice.
 - 2) To whom the nature of the study has been described and the subject or subject's parent/legal representative has provided written informed consent.
 - 3) Whom the investigator believes that the subject can and will comply with the requirements of the protocol.
 - 4) Who are in good health as determined by the outcome of medical history, physical

	CONFIDENTIAL :	Last Update Date
	THIS DOCUMENT AND INFORMATION CONTAINED HEREIN IS PROPRIETARY TO COMPANY AND IS NOT TO BE DISCLOSED WITHOUT THE WRITTEN PERMISSION OF COMPANY.	20-APR-2018
STATISTICAL ANALYSIS PLAN(V6.0)		

assessment and clinical judgment of the investigator.

[Exclusion criteria]

- 1) Contraindication, special warnings and/or precautions, as evaluated by the investigators, reported in the MenACWY-CRM conjugate vaccine Korean prescribing information
 - 2) Infants who were already enrolled in this trial for previous vaccination.
- (6) Subjects who prescribed off-label dosage:
- Vaccine schedule for children from 2 to 23 months of age :
 - Infants 2 to 6 months of age : Three doses of MenACWY-CRM, each of 0.5 ml, is to be given with an interval of at least 2 months; the fourth dose schedule be administered during the second year of life with an interval of at least 6 months after the third dose.
 - Infants 7 to 23 months of age : MenACWY-CRM is to be administered as two doses, each as single dose (0.5ml), with the second dose administered in the second year of life and at least three months after the first dose.
 - 2 to 55 years of age : MenACWY-CRM is to be administered as a single dose (0.5ml).
 - * The infant from 2 to 23 months of age may enroll at any point, in the vaccination series, including those subjects who may already initiated vaccination series. According to parental consents, these subjects may be followed up for 29 days within the surveillance period after subsequent vaccination(s) at the same study site.

Non-Safety per protocol set

Subjects excluded from safety per protocol set except for subjects who did not receive MenACWY-CRM and follow-up failure.

Based on rules for estimation of each number of safety evaluation cases, the following local regulation and Guideline on Standards for re-examination for new drugs, etc of MFDS, non-safety analysis set are excluded from the safety analysis set:

Guideline on Standards for re-examination for new drugs, etc (Chapter II, no. 3)

Patient Population for Surveillance:

- A) Patients planned to receive a drug under surveillance by investigator's medical judgment shall be subject.
- B) Subject who do not use within approved range shall not be included in the subject in principal.

However, if data of subject whose use is beyond approved range is collected, perform analysis as a separate item.

	CONFIDENTIAL :	Last Update Date
	THIS DOCUMENT AND INFORMATION CONTAINED HEREIN IS PROPRIETARY TO COMPANY AND IS NOT TO BE DISCLOSED WITHOUT THE WRITTEN PERMISSION OF COMPANY.	20-APR-2018
STATISTICAL ANALYSIS PLAN(V6.0)		

C) Describe actual selection methods of subject in detail.

3.2 Efficacy Analysis Set

Not Applicable

4. Endpoints

4.1 Safety Endpoints

Safety will be assessed after administration of study vaccine in terms of the number and percentage of subjects with:

- Local and systemic solicited adverse events reported from study Day 1 (day of vaccination) through study Day 7 post-vaccination;
- Unsolicited AEs reported from study Day 1 (day of vaccination) through study Day 7 post-vaccination;
- Medically attended AEs reported from study Day 1 to study termination (Day 29/early termination);
- SAEs reported from study Day 1 to study termination (Day 29/early termination).

5. Assessment Criteria

5.1 Safety Assessment Criteria

Not Applicable

	CONFIDENTIAL :	Last Update Date
	THIS DOCUMENT AND INFORMATION CONTAINED HEREIN IS PROPRIETARY TO COMPANY AND IS NOT TO BE DISCLOSED WITHOUT THE WRITTEN PERMISSION OF COMPANY.	20-APR-2018
STATISTICAL ANALYSIS PLAN(V6.0)		

6. Statistical Analyses

6.1 Baseline Characteristics

Descriptive statistics (mean, standard deviation, median, minimum and maximum) for baseline characteristics such as age, height and weight at enrollment will be calculated in the Safety set and Safety per Protocol set.

The following baseline characteristics will be reported:

< Subject Baseline Information >

- gender, age, ethnic origin, children group, weight, height, past diagnosis, kidney disorder, liver disorder, pre-Immunization temperature, temperature location, pregnancy

< Study Vaccine Information >

- vaccine site, number of previous Menveo, study vaccination number, concomitant medications

6.2 Safety Analyses

The number of subjects of AE[†] and the number of AEs[†] incurred shall be calculated, the incidence proportion of AEs[†] and its 95% confidence interval will be calculated using the normal approximation on the safety set and safety per protocol set.

† AE : AE includes solicited and unsolicited AE (DAY 1-7), medically attended AE (DAY 1-29) and SAE (DAY 1-29).

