2.2 Number of Subjects

A total of approximately 3,960 subjects are planned for enrolment into this study.

Assuming a 10% drop-out rate, this should provide approximately 3,000 evaluable subjects in the cohort 2 to 55 years of age and 600 in the cohort 2 to 23 months of age. This sample size meets the post-licensure requirements of the MFDS to provide continued safety monitoring in the Korean population.

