6.2.1 Adverse Events by Baseline Characteristics

AE[†]s (as described below) will be reported (n %) for the following baseline characteristics in the safety set and safety per protocol set :

- Age group (2-23 months, 2-10, 11-18, 19-34, 35-55, 55-64)
- Children group (<18, ≥18)
- Gender (male, female)
- Past diagnosis (yes, no)

	CONFIDENTIAL :	Last Update Date
	THIS DOCUMENT AND INFORMATION CONTAINED HEREIN IS PROPRIETARY TO COMPANY AND IS NOT TO BE DISCLOSED WITHOUT THE WRITTEN PERMISSION OF COMPANY.	20-APR-2018
STATISTICAL ANALYSIS PLAN(V6.0)		

- Temperature location (axillary, oral, rectal, ear)
- Administration site (left deltoid, right deltoid, left thigh, right thigh, other)
- Concomitant medication (yes, no)
- Kidney disorder (yes, no)
- Liver disorder (yes, no)
- Pregnancy (yes, no)
- Number of previous Menveo (0, 1, 2, 3)
- Study vaccination number (1, 2, 3, 4)

The n(%) of AEs[†] and its 95% confidence interval will be calculated using the normal approximation and analyzed using χ^2 - test. If more than 20% of expected frequencies of the cell counts are less than 5, Fisher’s exact test will be used instead of the chi-square test.

† AE : AE includes solicited and unsolicited AE (DAY 1-7), medically attended AE (DAY 1-29) and SAE (DAY 1-29).

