6.3 Additional Analyses for DDS (Data Disclosure Shell)

The following will be presented in the Safety set and Safety per Protocol set.

- Frequency and percentage by Age group (2-23 months, 2-10, 11-18, 19-64) will be presented.
- Frequency and percentage by study termination and reason not completed will be presented.
- The number of subjects of Non-SAE and the number of Non-SAE incurred shall be calculated, the incidence proportion of Non-SAE and its 95% confidence interval will be calculated using the normal approximation.
- The number of death resulting from AE shall be calculated.
- The number of subjects and percentage of Non-SAE will be calculated according to the preferred terms.

6.4 Additional Analyses for AE in the Local Product Label (Unsolicited AE Day 1-29)

The following will be presented in the Safety set and Safety per Protocol set.

- Preferred terms of Serious AE/ADR, unexpected AE/ADR will be presented respectively according to the proportion of AE in the local product label.

	CONFIDENTIAL :	Last Update Date
	THIS DOCUMENT AND INFORMATION CONTAINED HEREIN IS PROPRIETARY TO COMPANY AND IS NOT TO BE DISCLOSED WITHOUT THE WRITTEN PERMISSION OF COMPANY.	20-APR-2018
STATISTICAL ANALYSIS PLAN(V6.0)		

7. List of Table and Data Listings

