7.4 Additional Analyses for DDS (Data Disclosure Shell)

- Frequency and percentage by Age group (2-23 months, 2-10, 11-18, 19-64)
- Frequency and percentage by study termination and reason not completed
- Incidence proportion and the number of Non-SAE
- The number of death resulting from AE (frequency and percentage)
- Incidence proportion and number according to the preferred terms of Non-SAE (frequency and percentage)

7.5 Additional Analyses for AE in the Local Product Label (Unsolicited AE Day 1-29)

- Preferred terms of Serious AE/ADR, unexpected AE/ADR will be presented respectively according to the proportion.

	CONFIDENTIAL :	Last Update Date
	THIS DOCUMENT AND INFORMATION CONTAINED HEREIN IS PROPRIETARY TO COMPANY AND IS NOT TO BE DISCLOSED WITHOUT THE WRITTEN PERMISSION OF COMPANY.	20-APR-2018
STATISTICAL ANALYSIS PLAN(V6.0)		

8. Notes

- Each statistical analysis will be carried out with SAS Software version 9.4 or more recent version.
- In the descriptive statistics, mean, SD, minimum, median, and maximum will be calculated for continuous variables, and frequency and percentage for categorical variables.
- Data including sign of inequality such as “ ≥ 20 ”, “ > 20 ” will be excluded from analysis.
- All test statistics will be the results of two-sided tests with the statistical significant level of 0.05.
- The followings shall be included only in re-examination report:
 - Analysis by type of concomitant medications
 - Item ② of paragraph 6.2.3
 - Estimation of 95% confidence interval for incidence proportion of AEs by background factors
 - Paragraph 6.3, 6.4

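### The SAP prescribes normal-approximation 95% intervals for adverse-event proportions, SAEs included, with no rule for few or zero events, so zero SAEs would be reported as 0% to 0%

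*SAP*

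**What the plan says.** All references are to SAP V6.0 unless another version is named.

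- Section 6.2 sets the method for the incidence proportion of adverse events: "and its 95% confidence interval will be calculated using the normal approximation on the safety set and safety per protocol set". The footnote defines the term: "AE includes solicited and unsolicited AE (DAY 1-7), medically attended AE (DAY 1-29) and SAE (DAY 1-29").
- Section 6.2.1 applies the same method within each baseline characteristic, including kidney disorder, liver disorder, pregnancy and age 55-64: "95% confidence interval will be calculated using the normal approximation and analyzed using" a chi-square test. If more than 20% of expected cell counts are below 5, Fisher's "exact test will be used instead of the chi-square test". That rule covers the test only.
- Section 6.3 uses the same interval for non-serious events: "the incidence proportion of Non-SAE and its 95% confidence interval will be calculated using the normal approximation".
- Section 4.1 lists SAEs as a safety endpoint: "SAEs reported from study Day 1 to study termination (Day 29/early termination").
- Section 8 (Notes) restricts one item to the re-examination report: "Estimation of 95% confidence interval for incidence proportion of AEs by background factors".

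The last table shells in the documents are in Appendix 1 of SAP V4.0. Tables 2.1.1 and 2.2.1 there give SAE and Death their own pooled rows, with 95% CI columns for AE and for ADR, footnoted as normal approximation. The tables by system organ class and preferred term, and the tables by age, have no CI column. Neither the protocol nor any SAP version supplied states an exact, score or zero-event interval.

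**The concern.** Read in the usual way, the normal approximation is the Wald interval: the observed proportion plus or minus 1.96 estimated standard errors. With no events the estimated standard error is zero, so the interval has no width. With one to three events the lower limit is negative and the upper limit is too low.

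This is a single-arm, descriptive study with no hypothesis, so its estimates and their limits are its output. For a rare harm the informative part is the upper limit, meaning how large a risk the data still allow. The SAP recognises sparse data when it chooses a test, but it leaves the interval in the same paragraph unprotected. Two places are exposed: the pooled SAE and Death rows, and any-AE proportions in small baseline subgroups.

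**Working it through.** **Denominator.** Section 2.2 expects "3,000 evaluable subjects in the cohort 2 to 55 years of age and 600 in the cohort 2 to 23 months of age", so n = 3,000 + 600 = 3,600. I assume all of them are in the Safety Set. The planned enrolment of 3,960 equals 3,600 × 1.10; taking 10% off 3,960 leaves 3,564, which does not change the results materially. The SAE row is pooled over age in the V4.0 shells, so 3,600 is the relevant n, not a cohort size.

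**Formulas.** For x events in n:
- Wald: p ± 1.96 √(p(1−p)/n), with p = x/n.
- Clopper-Pearson: lower = Beta(0.025; x, n−x+1), upper = Beta(0.975; x+1, n−x). At x = 0 the upper limit is 1 − 0.025^(1/n).

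**Zero events.** Wald: 0 ± 1.96 × 0 = 0% to 0%. Exact: 1 − 0.025^(1/3600) = 0.102%.

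**One event.** p = 1/3600 = 0.0278% and the standard error is 0.0278%. Wald: 0.0278 ± 1.96 × 0.0278 = −0.027% to 0.082%. Exact: 0.001% to 0.155%.

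| Events (n = 3,600) | Wald 95% CI (%) | Exact 95% CI (%) | Wald upper / exact upper |
|---|---|---|---|
| 0 | 0 to 0 | 0 to 0.102 | 0 |
| 1 | −0.027 to 0.082 | 0.001 to 0.155 | 0.53 |
| 2 | −0.021 to 0.133 | 0.007 to 0.201 | 0.66 |
| 3 | −0.011 to 0.178 | 0.017 to 0.243 | 0.73 |
| 4 | 0.002 to 0.220 | 0.030 to 0.284 | 0.77 |

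**Coverage.** No expected SAE risk is given, so a range is assumed. Coverage is the sum of binomial probabilities over the counts whose interval contains the true risk.

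| Assumed true risk | P(0 events) | P(0 to 3 events) | Wald coverage | P(upper limit below true risk) | Exact | Wilson |
|---|---|---|---|---|---|---|
| 0.05% | 17% | 89% | 83.2% | 16.5% | 99.0% | 96.4% |
| 0.1% | 3% | 52% | 87.0% | 12.6% | 98.8% | 96.9% |
| 0.2% | <0.1% | 7% | 92.1% | 7.2% | 97.8% | 96.1% |

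The nominal chance that the upper limit falls below the true risk is 2.5%. At higher assumed risks, Wald coverage is 90.5% (0.3%), 93.7% (0.4%), 93.5% (0.5%) and 93.4% (1%). For common events, at 2%, 5% and 10%, it is 94.5%, 94.7% and 94.8%.

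**Small subgroups.** The documents give no sizes, so n = 10, 20 and 50 are assumed. With zero events Wald again gives 0% to 0%, against exact upper limits of 31%, 17% and 7%. Wald coverage is 65%, 88% and 88% at an assumed any-AE risk of 10%, and 84%, 95% and 93% at 30%.

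**The case against.** The strongest reply has four parts.

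1. *Scope.* Section 6.2 could mean a single interval for the composite any-AE proportion, where the approximation works. V6.0's own SAE text asks for counts and percentages by preferred term without a CI, and the SAE row with CI columns is visible only in the V4.0 shells. It is true that the V6.0 shells are not available. But the composite reading does not fit those shells, where SAE and Death are separate rows under CI columns with this footnote, and the V6.0 footnote to 6.2 still names SAEs.
2. *Wording.* The SAP does not name Wald or say whether negative limits are truncated. A Wilson interval would not collapse at zero events. If Wilson is intended, naming it settles the point. A continuity-corrected Wald interval would still give an upper limit of only 0.014% at zero events with n = 3,600.
3. *Likelihood.* The 0% to 0% result needs zero events, which has a probability of 17% at a risk of 0.05% and 3% at 0.1%. The SAE definition includes any hospitalisation whatever the cause, so the true risk may be higher. This stands, and above 0.2% the defect is smaller, though at assumed risks of 0.3% to 1% coverage is still only 90.5% to 93.7%.
4. *Consequence.* The endpoints are numbers and percentages, the protocol's safety analysis sections ask for no CI, and the counts are tabulated, so anyone can recompute. Subgroup intervals appear only in the re-examination report, and since enrolment requires good health some of those cells may be empty. All of this stands. It limits the weight of the point, but it does not make a zero-width or negative interval correct.

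**Conclusion.** The concern holds. Followed as written, the SAP gives wrong error bars for SAEs whenever they are few: no stated uncertainty at zero events, and upper limits at 53% to 73% of the exact ones at one to three events. In absolute terms the shortfall in the upper limit is 0.07 to 0.10 percentage points (0.102 − 0 at zero events, 0.243 − 0.178 at three). Nearly all the misses understate risk.

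This rests on reading normal approximation as Wald, on about 3,600 subjects in the pooled row, on assumed SAE risks of 0.05% to 0.2%, and on the SAE and Death rows of V4.0 having been kept. The subgroup figures also rest on assumed sizes. Common adverse events are not materially affected. It is a reporting defect that should be fixed, and it does not endanger the study's conclusions.

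**What to change.** In sections 6.2 and 6.2.1, replace the normal approximation with the exact (Clopper-Pearson) or Wilson interval, at least for SAEs, serious ADRs, deaths and baseline-subgroup proportions. Clopper-Pearson is conservative here, with coverage of 97.8% to 99.0% at the three assumed risks; Wilson stays nearer nominal, at 96.1% to 96.9%. Either is acceptable if it is named. Make the same change in section 6.3 and the table footnotes for consistency only: the 6.3 interval concerns non-serious events, which are common, and deaths there are only counted.

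The cost is one phrase in three sections, the footnotes and one SAS option. Data collection, sample size and conduct do not change. At n = 3,600 exact intervals are about 3% wider than Wald at an incidence of 2%, and about 1% wider at 10%.

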3.2 Discussion of Overall Study Design

This is a multicenter post-marketing surveillance study to monitor the safety of MenACWY-CRM in Korean individuals from 11 to 55 years of age receiving MenACWY-CRM vaccination according to routine clinical practice and prescribing information.

A total of approximately 3,300 subjects are planned for enrolment into this study, within a 6 years period. Assuming a 10% drop-out rate, this should provide approximately 3,000 evaluable subjects, in compliance with KFDA requirements. Clinics and hospitals including pediatricians and family doctors will be involved in the study.

The study is a post-licensure requirement of the KFDA to provide continued safety evaluation after immunization with MenACWY-CRM in the Korean population.

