6.2.3 Adverse Events²

An adverse event (AE) is defined as any untoward medical occurrence in a subject or clinical investigation subject administered a pharmaceutical product at any dose that does not necessarily have to have a causal relationship with this treatment. An AE can, therefore be any unfavorable and unintended sign (including an abnormal laboratory finding, for example), symptom, or disease temporally associated with the use of an investigational product, whether or not considered related to the investigational product. This definition includes intercurrent illnesses or injuries and exacerbation of pre-existing conditions.

An unexpected adverse event is one that is not listed in Package Leaflet or an event that is by nature more specific or more severe than a listed event.

The severity of events reported on the “Adverse Events” CRF will be determined by the investigator as:

Mild: transient with no limitation in normal daily activity.
Moderate: some limitation in normal daily activity.
Severe: unable to perform normal daily activity.

The relationship of the study treatment to an AE will be determined by the investigator based on the following definitions:

1. Not Related

The AE is not related if exposure to the investigational vaccine has not occurred, **or** the occurrence of the AE is not reasonably related in time, **or** the AE is considered unlikely to be related to use of the investigational vaccine, i.e. there are no facts (evidence) or arguments to suggest a causal relationship.

2. Possibly Related

The administration of the investigational vaccine and AE are considered reasonably related in time **and** the AE could be explained by causes other than exposure to the investigational vaccine.

² Adverse Events collected in this study and that are not solicited on a checklist may also be referred to as “unsolicited Adverse Event” in the Clinical Study Report.

3. Probably Related

Exposure to the investigational vaccine and AE are reasonably related in time **and** the investigational vaccine is more likely than other causes to be responsible for the AE, **or** is the most likely cause of the AE.

The relationship of the study treatment to an AE will be determined by the investigator.

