2.4 Study Method

In order to obtain information on Regulatory PMS data after-market launch, or delegate will create the Regulatory PMS contract with the relevant clinics/hospitals and the physician in charge of the survey shall implement this Regulatory PMS in subjects that receive MenACWY-CRM in the relevant hospital/clinic since the contract date until the number of contracted survey cases, without omission, is reached.

Overview of Study Design

This is a multicenter post marketing surveillance study to monitor the safety of MenACWY-CRM administered according to the prescribing information to 3,960 healthy subjects from 2 months to 55 years of age in Korea.

Subjects will be enrolled at the time of their visit to a participating clinic or hospital for vaccination with MenACWY-CRM according to the routine clinical care.

	CONFIDENTIAL :	Last Update Date
	THIS DOCUMENT AND INFORMATION CONTAINED HEREIN IS PROPRIETARY TO COMPANY AND IS NOT TO BE DISCLOSED WITHOUT THE WRITTEN PERMISSION OF COMPANY.	20-APR-2018
STATISTICAL ANALYSIS PLAN(V6.0)		

At Visit 1 (Day 1), after obtaining consent from the subjects or subjects’ parents/legal representative (and Assent Form, if required by the relevant IRB), the vaccination will be administered. Subjects will remain under observation for at least 30 minutes in the clinic after study immunization.

The subjects or subject’s parent/legal representative will be then instructed to complete the Diary Card daily, reporting local and systemic adverse events and all other AEs occurring within 7 days following immunizations, and medically attended AEs or SAEs occurring up to Day 29 within the surveillance period after each study vaccination.

Subjects will also be instructed to return the completed diaries to the study site at Day 29 as follows:

- During a visit at the study center or
- Using the provided pre-addressed stamped envelope (PASE).

At the investigator discretion, the subject or subject’s parent/legal representative will be reminded of the date of the study termination by a phone call at Day 29. If any clarification is required after Diary Card retrieval the site staff will follow up by phone, and any additional finding will be recorded on the subject’s medical record.

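### The planned 95% CIs and tests take no account of clustering by contracted clinic, so precision for common events may be overstated by an amount the plan does not allow one to determine

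*SAP*

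**What the plan says.** **Recruitment.** SAP V6.0 section 2.4 has the sponsor contract clinics and hospitals, after which "the physician in charge of the survey shall implement this Regulatory PMS in subjects that receive MenACWY-CRM in the relevant hospital/clinic since the contract date"; enrolment stops once a site has its contracted number. Protocol 3.2 describes the mix of sites: "Clinics and hospitals including pediatricians and family doctors will be involved in the study". Under Protocol 3.3.3 the first three digits of each subject number are the site code.

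**Size and purpose.** SAP V6.0 section 2.2: "A total of approximately 3,960 subjects are planned for enrolment into this study", intended to yield "approximately 3,000 evaluable subjects in the cohort 2 to 55 years of age and 600 in the cohort 2 to 23 months of age". The same section ties this number to the regulator's requirement for safety monitoring in Korea as a whole.

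**Analysis.** Section 6.2 gives AE proportions whose "95% confidence interval will be calculated using the normal approximation on the safety set and safety per protocol set". Section 6.2.1 applies the same interval and a chi-square test across 12 background factors, moving to Fisher's exact test under a cell-count rule: "If more than 20% of expected frequencies of the cell counts are less than 5". Section 6.3 repeats the normal-approximation interval for non-serious AEs: "The number of subjects of Non-SAE and the number of Non-SAE incurred shall be calculated". Section 8 sets two-sided tests at 0.05. No site term, cluster variance, by-site table or design effect appears in the protocol or SAP text available.

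**Who records and judges.** Subjects or parents record solicited events on the Diary Card. For adverse events, Protocol 6.2.3 states: "The relationship of the study treatment to an AE will be determined by the investigator". The investigator also grades the severity of events on the Adverse Events CRF.

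**The concern.** Subjects from one clinic may resemble each other more than subjects from different clinics, for two or three reasons.

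- **Case mix.** Paediatric and family practices see different ages, and the solicited lists and the millimetre bands for erythema and induration change at age 6.
- **Ascertainment.** Each site instructs its own subjects, reviews their diaries and makes the follow-up calls (Protocol 3.3 and 6.2.2).
- **Judgement.** Each investigator decides causality, which defines an ADR in SAP 6.2.3.

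The first two can reach solicited events. The third bears on unsolicited AEs and ADRs.

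The study has no comparator and no hypothesis (Protocol 7.1), so a proportion with its CI is the result itself. If the interval is read as a statement about Korean vaccinees, variation between clinics belongs in it. A test of a factor that mostly separates one kind of clinic from another inherits the same omission.

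**Working it through.** **The plan's own figure.** 3,000 + 600 = 3,600 evaluable subjects. 3,600 × 1.1 = 3,960, the planned enrolment. Forward, 3,960 × 0.9 = 3,564, which is 1.0% below 3,600. So about 3,600 is the right N. The documents give no CI width, coverage or design effect to reproduce.

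**Assumed inputs (not in the documents).** Sites G = 20, 50, 100 or 200, of equal size; ICC 0.001, 0.01 or 0.05; a common-event proportion of 30%.

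**Formulas.** Mean site size m = 3,600/G. Design effect DE = 1 + (m − 1) × ICC. Coverage of the planned interval = 2Φ(1.96/√DE) − 1. Example: G = 20 gives m = 180; at ICC 0.01, DE = 1 + 179 × 0.01 = 2.79, 1.96/√2.79 = 1.173, and coverage is 75.9%.

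| Sites (m) | ICC 0.001: DE, coverage | ICC 0.01: DE, coverage | ICC 0.05: DE, coverage |
|---|---|---|---|
| 20 (180) | 1.179, 92.9% | 2.79, 75.9% | 9.95, 46.6% |
| 50 (72) | 1.071, 94.2% | 1.71, 86.6% | 4.55, 64.2% |
| 100 (36) | 1.035, 94.6% | 1.35, 90.8% | 2.75, 76.3% |
| 200 (18) | 1.017, 94.8% | 1.17, 93.0% | 1.85, 85.0% |

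**Width.** At 30%, the planned half-width is 1.96 × √(0.3 × 0.7/3,600) = 1.50 points. At ICC 0.01 it should be 1.50 × √DE: about 2.50 points (20 sites), 1.96 (50) or 1.74 (100).

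**What these ICCs mean.** At 30%, the between-clinic SD is √(ICC × 0.21): 1.4 points at ICC 0.001, 4.6 at 0.01 and about 10 at 0.05. Coverage falls to 90% when DE = (1.96/1.645)² = 1.42. That needs an ICC of 0.0023 with 20 sites, 0.0059 with 50, 0.012 with 100 or 0.025 with 200.

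**Simulation check.** Beta-binomial data, 30% proportion, 50 equal sites: coverage 94.5%, 87.0% and 65.0% at the three ICCs, in line with the table. Unequal sites were worse: 69.5% at ICC 0.01 in the one skewed layout drawn.

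**Infant cohort (N = 600).** With 20 sites, m = 30 and coverage is 91.6% at ICC 0.01 and 78.9% at 0.05.

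**Tests.** Simulated rejection at nominal 5% (3,600 subjects, 40 sites, ICC 0.05): 4.8% for a factor balanced within sites, 21.9% for an 80/20 split between two kinds of site, 40.1% for a factor fixed by site.

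**Rare rows.** Suppose clinics differ by the same relative amount at every incidence. ICC 0.01 at 30% is a relative SD of 4.58/30 = 0.153, squared 0.0233. At an incidence of 0.1% this gives ICC = 0.0233 × 0.001/0.999 = 0.000023. With 20 sites, DE = 1 + 179 × 0.000023 = 1.004.

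**The case against.** A reader might infer that the planned intervals do cover well below 95%. The documents do not support that. It needs a site count and an ICC, and neither is given. With near-identical clinics, or with many small ones and a modest ICC, coverage stays at about 93-95%.

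A reader might also infer that investigator judgement clusters the solicited events. Those are recorded by subjects or parents against fixed bands and verbal definitions, so that route mainly concerns unsolicited AEs and ADRs. Site review of diaries and differences in case mix remain as possible sources for solicited events.

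Three further arguments carry weight.

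- **Target of inference.** Sites are contracted, not randomly drawn. Conditional on the contracted sites, the binomial variance is not too small. Treating sites as a sample of Korean clinics is a modelling choice, though the population-level purpose in SAP 2.2 favours it.
- **Age.** In the last table shells available (SAP V4.0 Appendix 1, Tables 2.1.1 and 2.2.1), solicited CIs are split at 2-23 months, 2-5 years and 6 years or over, which removes part of the case-mix effect. The unsolicited, MAAE and total rows are not split.
- **Consequence.** The analyses are descriptive, and no decision rule or precision target uses the CIs. Background-factor CIs and all of 6.3 go only into the re-examination report (section 8).

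Finally, the Appendix 1 cited in V6.0 is not in the available text, so the absence of site-level output can be stated only for what is visible.

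**Conclusion.** The point holds conditionally. The planned CIs and tests ignore the clinic level. If AE proportions vary between clinics, intervals for solicited AE, any AE, ADR and non-serious AE are too narrow for inference beyond the enrolled sites, and tests of factors tied to clinic type can be anti-conservative. Over the assumed range (ICC 0.001 to 0.05, 20 to 200 equal sites, N = 3,600), coverage runs from 94.8% down to 46.6%. Nothing in the documents says where in that range the study lies; its own data can.

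The effect on SAE and death rows is small, provided relative variation between clinics is not much larger for rare events. Those rows have a separate problem: the normal approximation under-covers at low counts even without clustering (about 87% at a 0.1% proportion). Factors balanced within clinics, such as gender if it is so balanced, are not inflated.

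This calls for an inexpensive addition to the analysis. It does not invalidate the reported proportions, nor does it justify replacing the variance in every row.

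**What to change.** - **Sections 6.2 and 6.3.** For the common-event rows, prespecify a site-clustered 95% CI beside the planned one: Taylor linearisation with site as the cluster and t with (sites − 1) degrees of freedom, for example SAS PROC SURVEYFREQ with a CLUSTER statement. Report the number of sites and the design effect next to each of these proportions.
- **Section 6.2.1.** For factors that differ between clinics, give the Rao-Scott chi-square beside the ordinary test.
- **Interpretation.** State that precision will be judged on the clustered interval where the design effect is materially above 1, and fix the threshold in advance. As a guide, a design effect of 1.17 corresponds to 93% coverage of the planned interval and 1.42 to 90%.
- **Exclusion.** Do not use linearised intervals for rare or zero-event rows. With no events the linearised variance is zero.

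**Cost.** Some SAP wording and one further SAS procedure. No new data, visits or subjects are needed. Reported intervals may widen, and the cluster variance is slightly unstable with few sites. In simulation (3,000 subjects, 40 unequal sites, ICC 0.05, 30% proportion) the planned interval covered 55.3% with a half-width of 1.6 points, against 93.5% and 4.2 points for the clustered one. With 20 unequal sites the clustered interval covered about 92.5%.
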